### 5.3 Sample Size

This study will enroll up to 50 subjects who will undergo one (1) study visit that will last approximately one (1) hour. The analysis population will include a minimum of 37 subjects. Up to 50 subjects will be consented and enrolled.

## 6.0 mobiCARE Placement Methodology

[figure not shown]
1. The optimal position of the Main Body (top) electrode is horizontally 2.5cm right of the chest's midline, and vertically in the 3rd intercostal space.
2. The optimal position of the Battery Body (bottom electrode) is horizontally equivalent to the middle of the left clavicle, and vertically in the 5th intercostal space (corresponding the the V4 position)
3. The evaluation will include three (3) different alternate locations for the mobiCARE ECG

Monitoring System are as follows. All locations are to monitor the heart rhythm in Lead II.

**Table 1. Three Different Placement Locations in Addition to Nominal**

Alternate Location	Main Body (Top Electrode)	Battery Body (Bottom Electrode)
1	Horizontally 1 cm left	Horizontally 1 cm right
	Vertically 1 cm inferior	Vertically 1 cm superior
2	Horizontally 1 cm left	Horizontally 1 cm right
	Vertically 3.6 cm superior	Vertically 3.6 cm anterior
3	Horizontally 3.6 cm right	Horizontally 3.6 cm left
	Vertically 1 cm inferior	Vertically 1 cm superior

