**Figure 1. Three Alternative mobiCARE Electrode Positions As Located on the Torso**

[figure not shown]

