### 10.4 Primary and Secondary Objectives

#### 9.4.1 Primary Objective

The primary objective is to quantify the placement accuracy requirements (i.e., cm/in offset may be tolerated from the nominal placement position) needed to ensure appropriate device performance including heart rhythm interpretability and provide rationale to support that such placement accuracy is adequate.

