## 10.5 Primary Endpoints and Secondary Endpoints

### 10.5.1 Primary Endpoint

Evaluation of the ECG signal at the nominal location and in up to three (3) additional standardized locations in each subject to determine if the signal is interpretable. The term “interpretable” is defined as follows: An independent cardiologist is able to identify the ECG rhythm in each location when compared to the ECG rhythm measured in the nominal position of the mobiCARE™ ECG Monitoring System described in the Instructions for Use. ECG rhythm data will be collected for up to two (2) minutes while the patient ambulates.

The simultaneous Holter Monitor will be evaluated at the same time points to have a point of reference for the mobiCARE™ system in the case that changes in the rhythm are noted during the study.

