### 11.2 Analysis of Primary Endpoint

The primary endpoint will be analyzed using an asymptotic non-inferiority test for the difference in interpretability of the ECG signal between two correlated proportions. The test is described in the references and discussed in references. The null and alternative hypotheses are

$$H_0: P_A - P_N \leq -M_{NI} \text{ and } H_A: P_A - P_N > -M_{NI}$$

where  $P_N$  and  $P_A$  are the proportions of measurements with interpretable ECG results at the nominal position and each alternative location, respectively, and  $M_{NI}$  is the positive non-inferiority margin. This one-sided test will be performed with type I error rate  $\alpha = 0.025$  and non-inferiority margin  $M_{NI} = 0.20$ . The test will be repeated for each alternative location, comparing it to the nominal position. No adjustment will be made for multiple comparisons.

Uninterpretable ECG at one location does not constitute a failure for that subject.

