**30.3 APPENDIX 3 – Use Steps and Limited Human Factors Assessment**

30.3.1 Administrative and Healthcare Professional Use Steps for Mobile – ECG Clinical Study

30.3.2 Healthcare Professional and Subject Human Factors Assessment (n=15 Subjects)

**Appendix 30.3.1 Administrative and Healthcare Professional Use Steps for Mobile – ECG Study**

*Attached separately in PDF Format*

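### Table 1 gives the vertical shift of the Location 2 bottom electrode as anterior, which is not a vertical direction, so one coordinate of a primary test position is not validly stated

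*Combined protocol and SAP*

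**What the plan says.** Section 6.0 locates each electrode on two axes, horizontal and vertical. The nominal bottom electrode, for example, is "horizontally equivalent to the middle of the left clavicle, and vertically in the 5th intercostal space". The vertical axis is thus the head-to-foot axis, marked by intercostal space.

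Table 1 then defines three alternate locations as horizontal and vertical shifts of the top (Main Body) and bottom (Battery Body) electrodes. At Location 2 the top electrode moves "Vertically 3.6 cm superior" and the bottom electrode moves "Vertically 3.6 cm anterior". The remaining vertical entries, at Locations 1 and 3, are 1 cm inferior for the top electrode and 1 cm superior for the bottom.

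Two other sources may show the same positions: Figure 1, titled "Three Alternative mobiCARE Electrode Positions As Located on the Torso", and Appendix 30.3.1, "Administrative and Healthcare Professional Use Steps for Mobile", which is attached separately. Neither was available for this review. No other text in the protocol gives the Location 2 bottom position.

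**The concern.** The direction in this cell lies on neither of the two axes the protocol uses. The distance (3.6 cm), the horizontal shift (1 cm right) and the whole of the top-electrode entry are stated; the vertical direction of the bottom electrode is not.

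This matters because the offsets are what the study is about. The primary objective (Section 10.4, item 9.4.1) is to establish what "cm/in offset may be tolerated from the nominal placement position". The primary endpoint (Section 10.5.1) is read at "additional standardized locations in each subject to determine if the signal is interpretable". Section 11.2 adds: "The test will be repeated for each alternative location, comparing it to the nominal position". Location 2 therefore carries one of three primary comparisons, and it is the only location with a vertical shift larger than 1 cm. Any statement about vertical tolerance beyond 1 cm rests on this row, so its result needs to be attached to an offset that the protocol states correctly.

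**Working it through.** The plan gives no derived figure to reproduce here. The check has two parts: a comparison of the table entries and some simple geometry.

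**Inputs (Table 1).** Left and right are taken as the subject's own, consistent with the nominal description in Section 6.0.

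| Location | Axis | Top electrode | Bottom electrode | Opposite directions? |
|---|---|---|---|---|
| 1 | Horizontal | 1 cm left | 1 cm right | yes |
| 1 | Vertical | 1 cm inferior | 1 cm superior | yes |
| 2 | Horizontal | 1 cm left | 1 cm right | yes |
| 2 | Vertical | 3.6 cm superior | 3.6 cm *anterior* | cannot be judged |
| 3 | Horizontal | 3.6 cm right | 3.6 cm left | yes |
| 3 | Vertical | 1 cm inferior | 1 cm superior | yes |

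Five of the six vertical entries use a vertical direction; one does not. In all 5 of the other 5 top/bottom pairs the electrodes move in opposite directions and by equal distances. That is a cue to intent, though the protocol nowhere states it as a rule.

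**Distance from nominal along the chest surface**, √(horizontal² + vertical²):

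- Location 1, both electrodes: √(1² + 1²) = 1.41 cm
- Location 3, both electrodes: √(3.6² + 1²) = 3.74 cm
- Location 2, top: √(1² + 3.6²) = 3.74 cm
- Location 2, bottom, if superior or inferior: √(1² + 3.6²) = 3.74 cm
- Location 2, bottom, if the word is taken literally and there is no vertical shift: √(1² + 0²) = 1.00 cm

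The superior and inferior sites are 2 × 3.6 = 7.2 cm apart.

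**Change in separation of the electrode pair at Location 2.** The top electrode moves 3.6 cm up in every case.

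| Reading of the bottom entry | Change in vertical separation |
|---|---|
| Inferior | 3.6 + 3.6 = +7.2 cm |
| Superior | 3.6 − 3.6 = 0 cm |
| Literal, no vertical shift | 3.6 + 0 = +3.6 cm |

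Horizontal separation falls by 1 + 1 = 2 cm under all three readings, because each electrode moves 1 cm toward the other.

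**The case against.** The strongest reply is that this is an obvious one-word slip. Every other pair in the table moves in opposite directions, and the two Location 2 distances are equal, so the table itself favors one reading. The superior reading would make Location 2 the only place where both electrodes move the same way. The literal reading has to ignore both the 3.6 cm and the word for the axis in the same cell. The distance from nominal is 3.74 cm in either vertical direction, so an offset reported only as a distance would not change. Figure 1, the use steps and the site training that the protocol requires may leave operators in no doubt.

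Much of this stands. A slip is the likely explanation; the literal reading is weak, and the 1.00 cm figure should be given little weight. It cannot be shown that any operator would misplace the electrode or that Figure 1 disagrees with the table.

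It does not remove the point. Staff would have to infer a primary test coordinate from a pattern. The two vertical directions give the same distance but different sites and different pair separations, so distance alone does not describe what was tested. If Figure 1 or the use steps show a direction, the table still has to be brought into line with them. A fault in reading the PDF is also an unlikely explanation, because the cell is complete, with axis, distance and direction all present.

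**Conclusion.** The concern holds. As written, Table 1 does not validly state the vertical coordinate of the bottom electrode at Location 2. The extent is limited to one coordinate of one electrode at one of three locations. Between the two vertical directions, the electrode site differs by 7.2 cm and the change in vertical separation of the pair is either 0 cm or +7.2 cm.

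The type I error rate, the non-inferiority margin, power and sample size do not change, and no bias is claimed. The conclusion concerns the table text only. It does not say that the position is undefined across all study materials, since Figure 1 and the use steps were not seen. It should be fixed because the cell defines a primary test position, and the only 3.6 cm vertical shift, in a study meant to quantify tolerated offset.

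**What to change.** In Table 1, Location 2, Battery Body, the sponsor should replace *anterior* with the vertical direction it intends. It should then check that this cell, Figure 1 and the Appendix 30.3.1 use steps all show the same position. Both steps should be done before the first subject, so that no primary data are collected at a position the table misstates. The direction is for the sponsor to confirm; this review does not choose it.

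The cost is a one-word correction and a check of two companion items. Design, sample size and analysis stay as they are.

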Primary Objective	The primary objective is to quantify the placement accuracy requirements (i.e., how many cm/in. offset may be tolerated from the nominal placement position) needed to ensure appropriate device performance including heart rhythm interpretability and provide rationale to support that such placement accuracy is adequate.
Secondary Objective	The secondary objectives are to: 1. Demonstrate that the device meets the placement accuracy requirements when in normal use, and 2. Identify if there are factors that may impact the placement accuracy and subsequent heart rhythm identification such as age, sex, educational level, BMI, and dexterity.
Primary Endpoint	Evaluation of the ECG signal at the nominal location and in up to three (3) additional standardized locations in each subject to determine if the signal is interpretable. The term “interpretable” is defined as follows: An independent

	
cardiologist is able to identify the ECG rhythm in each location when compared to the ECG rhythm measured in the nominal position of the mobiCARE™ ECG Monitoring System described in the Instructions for Use. ECG rhythm data will be collected for up to two (2) minutes while the patient ambulates.
 
The simultaneous Holter Monitor will be evaluated at the same time points to have a point of reference for the mobiCARE™ system in the case that changes in the rhythm are noted during the study.

Secondary Endpoints (Informational Only)	
 
1. Presence of artifact graded as 1=none, 2=minor (cardiac rhythm is interpretable), or 3=major (cardiac rhythm is not interpretable by the independent cardiologist).
 
2. ECG Morphology measurements: P wave amplitude, QRS amplitude, QRS duration.
 
3. Limited Human Factors Evaluation Measures (n=15): 
 
A. Initial Healthcare practitioner (HCP) placement according to IFU (correct or incorrect placement when referring to the IFU)
 
B. User demonstrates ability to change electrodes (successful or not successful)
 
C. Observe user to determine sufficient dexterity for user to perform the task
 
D. Observe user electrode placement according to skin markings to determine if electrodes are correctly placed.
 
 
 

Participation Duration	Each subject will participate in this study for one (1) visit, for approximately 30 to 60 minutes.

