## 11.0 Statistical Considerations

### 11.1 Introduction

Each subject will have the mobiCARE™ ECG measured at the nominal position and at 3 pre-specified alternate locations. For each location, the ECG signal will be read and classified as interpretable or not interpretable. The reading from the mobiCARE™ nominal position will serve as the comparator reading for the alternate mobiCARE™ locations. The primary endpoint analysis is the comparison of each mobiCARE™ alternate location to the nominal position.

The Holter monitor will be used as a method to verify the subjects heart rhythm during simultaneous recordings of mobiCARE™ heart rhythm data at the prespecified measurement locations on the precordium.

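### The primary objective asks for a direction-free tolerance in cm, but Table 1 tests only three fixed offset combinations, one of which has an undefined direction, so only a per-location conclusion can be supported

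*Combined protocol and SAP*

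**What the plan says.** The synopsis (section 1.0) words the primary objective as finding "how many cm/in. offset may be tolerated from the nominal placement position". Section 9.4.1 has the same aim, "cm/in offset may be tolerated from the nominal placement position", and adds that the study should "provide rationale to support that such placement accuracy is adequate". Neither place names a direction.

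Section 6.0 sets the nominal position. The top electrode is "horizontally 2.5cm right" of the midline in the third intercostal space. The bottom electrode is "horizontally equivalent to the middle of the left clavicle" in the fifth. The pair therefore runs from upper right to lower left.

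Table 1 lists three alternates. For the top electrode, Locations 1 and 2 have "Horizontally 1 cm left" and Location 3 has "Horizontally 3.6 cm right". The bottom electrode mirrors each horizontal entry. The vertical entries mirror each other in Locations 1 and 3. In Location 2 the top electrode moves 3.6 cm superior, while the bottom electrode's vertical entry is 3.6 cm anterior.

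Section 11.1 states: "The primary endpoint analysis is the comparison of each mobiCARE™ alternate location to the nominal position". Section 11.2 repeats the non-inferiority test for each alternate. No section explains the choice of 1 and 3.6 cm or of the directions, or says how the three results combine into a tolerance.

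**The concern.** A tolerance stated only as a number of centimetres covers every direction of misplacement up to that distance. The table samples a few directions. If all three tests succeed, a report could say that 3.6 cm is tolerated, and nothing in the plan would restrain that wording.

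The figure would then be used. The first secondary objective (section 9.4.2) is to show that the device meets the placement accuracy requirements in normal use, and section 27.0 says the study will support a 510(k) submission. Section 11.4 describes placement by anatomic landmarks, with skin marking for home replacement left optional. A misjudged landmark could plausibly move both electrodes the same way, a pattern the table may not contain at all.

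The Location 2 cell adds a practical problem. As written, it gives the site no position for the bottom electrode, so the content of one of the three primary comparisons is uncertain.

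**Working it through.** The plan gives no cm tolerance to reproduce. The check classifies each offset in Table 1 against the nominal axis in section 6.0, taking left and right as the subject's. Inward means toward the other electrode: left and inferior for the top one, right and superior for the bottom one.

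**Step 1. Direction of each move (cm).**

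| Location | Top, horizontal | Bottom, horizontal | Top, vertical | Bottom, vertical |
|---|---|---|---|---|
| 1 | 1 inward | 1 inward | 1 inward | 1 inward |
| 2 | 1 inward | 1 inward | 3.6 outward | 3.6, direction undefined |
| 3 | 3.6 outward | 3.6 outward | 1 inward | 1 inward |

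Three of the four 3.6 cm entries are explicitly outward, none is explicitly inward and one is undefined. The largest horizontal inward move is 1 cm. Both electrodes move in every location.

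**Step 2. Size of each move.** The straight-line displacement per electrode is √(1² + 1²) = 1.41 cm in Location 1. In Location 3, and in Location 2 if the open cell is vertical, it is √(1² + 3.6²) = 3.74 cm. Each 3.6 cm component is paired with 1 cm inward on the other axis, so 3.6 cm outward is never tested alone or on both axes together.

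**Step 3. Whole-device shift.** The midpoint of the pair moves by half the sum of the two displacements. In Locations 1 and 3 every horizontal and vertical pair cancels, so the shift is 0. In Location 2 the horizontal pair cancels, (−1 + 1)/2 = 0, and the vertical part depends on the open cell:
- inferior: (3.6 − 3.6)/2 = 0 cm;
- superior: (3.6 + 3.6)/2 = 3.6 cm upward.

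So the number of locations with a same-direction shift is 0 of 3 or 1 of 3. The number with any inward move above 1 cm is also 0 of 3 or 1 of 3 (the bottom electrode, vertically). On both readings no location has a sideways or downward shift.

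**Step 4. Electrode spacing, illustrative only.** The documents give no nominal spacing. Assume the bottom electrode is 7 to 10 cm left of the midline, so the horizontal separation h is 9.5 to 12.5 cm (adding 2.5), and the vertical separation v is 5 to 9 cm. Spacing is √(h² + v²). The example uses h = 11 and v = 7, where nominal spacing is √(121 + 49) = 13.0 cm.

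| Location | Change in h, v (cm) | Example spacing (cm) | Change over the assumed range |
|---|---|---|---|
| 1 | −2, −2 | √(9² + 5²) = 10.3 | −18% to −25% |
| 2, if inferior | −2, +7.2 | √(9² + 14.2²) = 16.8 | +20% to +36% |
| 2, if superior | −2, 0 | √(9² + 7²) = 11.4 | −10% to −16% |
| 3 | +7.2, −2 | √(18.2² + 5²) = 18.9 | +36% to +58% |
| Not tested: 3.6 cm inward horizontally, 1 cm inward vertically | −7.2, −2 | √(3.8² + 5²) = 6.3 | −43% to −65% |

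Under these assumptions the tested shortening stops at about a quarter of the spacing on either reading, while the untested inward mirror of Location 3 would shorten it by more than 40%. Nothing in the documents links spacing to interpretability, so these percentages describe the coverage of the design, not a loss of performance.

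**The case against.** The strongest reply is that the plan nowhere claims a 3.6 cm tolerance. The endpoint is confined to standardised locations, each is tested on its own, and the objective already requires a rationale, where limits on direction could be stated. That stands as far as it goes: the overclaim is a risk in the report, not a statement in the plan. But the objective is worded as a general tolerance, and no section limits it.

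A second reply is that the chosen offsets are informative. With the open cell read as inferior, and under the geometry assumed above, Locations 2 and 3 rotate the lead axis in opposite senses by about 21 to 31 and 13 to 21 degrees, and Location 1 shortens the lead. A same-direction shift leaves the pair's length and angle unchanged. Preferring offsets that change the lead vector is a defensible choice. The documents do not make this argument, however. A whole-device shift still moves both electrodes relative to the heart, and the argument does not reach the larger inward moves.

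A reader might infer that all three alternates are certainly opposite moves, that 3.6 cm is tested only outward, or that both 3.6 cm locations lengthen the spacing. The table does not establish this. Each statement depends on reading the open cell as inferior, and Figure 1 is not visible in the copy reviewed. The mirrored pattern makes that reading the likelier one, but if the cell means superior all three statements fail.

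**Conclusion.** The point holds in limited form. The design can support a statement about each tested combination of offsets. It cannot support a cm tolerance without direction. Independently of the open cell, it leaves untested any horizontal inward move above 1 cm, any sideways or downward shift of the whole device, and any single-electrode offset. Whether it also leaves every whole-device shift untested depends on that cell, which defines no position as written.

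This rests on Table 1, section 6.0 and the wording of the objective. It does not rest on the spacing percentages. The three non-inferiority comparisons and the sample size of 37 are unaffected, since neither depends on how the offsets are later summarised. A reader might go further and conclude that the device fails in the untested directions, or that the trial is uninformative; the documents support neither.

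**What to change.** 1. Before enrolment, reconcile the vertical entry for the bottom electrode in Location 2 with the intended position and with Figure 1. The sponsor must say which position is meant.
2. In sections 9.4.1 and 11.2, and in the matching synopsis text, state that the conclusion will be given per tested location, as the exact combination of offsets and directions that met non-inferiority. State that no single direction-free figure will be claimed, and none for untested directions or whole-device shifts, unless a documented rationale shows that the tested offsets are worst case. Avoid wording such as up to 3.6 cm, which interpolates to offsets that were not recorded.
3. Carry the same wording into the report.

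This is a change of text only, with no added subjects or recordings. The downside is a narrower statement than one cm figure. If the sponsor wants a general figure, redefining one alternate as a same-direction shift would add no recording, but it would give up either the only all-inward test or one of the two 3.6 cm tests, and it would still not cover larger inward moves. It is a trade-off rather than a free repair.

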**Figure 1. Three Alternative mobiCARE Electrode Positions As Located on the Torso**

[figure not shown]
## 7.0 Holter Monitor Placement Location

The Holter monitor will be placed in one location recommended by the Holter Monitor Company (NorthEast Monitoring, Inc. Maynard, MA. USA) by the HCP for Lead II as indicated below.

Attach the ECG electrode patches for the Holter monitor to the Holter Monitor Leads. Snap the leads from the Holter monitor onto the electrodes. Remove the backing of one electrode and

place the electrode with red, white, or black lead wire in the corresponding location below. Complete these steps for the other two, one at a time. The white lead with electrode should be on the upper right, the black lead with electrode should be on the upper left, and the red lead with electrode should be on the lower left so that Lead II is a diagonal vector from upper right to lower left.

